7.2 Lost to follow-up

A subject will be considered potentially lost to follow-up if they fail to return for scheduled visits and are unable to be contacted by the study site.

The following actions must be taken if a subject fails to return to the study site for a required study visit:

- The site must attempt to contact the subject and reschedule the missed visit as soon as possible and counsel the subject on the importance of maintaining the assigned visit schedule.
- Before a subject is deemed lost to follow-up, the investigator or designee must make every effort to regain contact with the subject or next of kin (e.g. by repeat telephone calls, certified letter to the subject's last known mailing address or local equivalent methods). These contact attempts should be documented in the subject's medical record.
- Efforts to reach the subject should continue until the end of the study. Should the subject be unreachable at the end of the study, the subject should be considered to be lost to follow-up with unknown vital status at the end of the study and censored at the latest follow-up contact.

7.3 Withdrawal from the study

A subject may withdraw from the study (e.g. withdraw consent), at any time (IP **and** assessments) at his/her own request, without prejudice to further treatment.

A subject who considers withdrawing from the study must be informed by the investigator about modified follow-up options (e.g. telephone contact, a contact with a relative or treating physician, or information from medical records) per Section 7.1.3.

If the subject or his/her parent(s)/legal guardian withdraws consent for disclosure of future information, the sponsor may retain and continue to use any data collected before such a withdrawal of consent.

If a subject or his/her parent(s)/legal guardian withdraws from the study, he/she may request destruction of any samples taken, and the investigator must document this in the site study records.

A subject who withdraws consent will always be asked about the reason(s) and the presence of any AE. The investigator will follow up subjects as medically indicated.

AstraZeneca or its delegate will request investigators to collect information on subjects' vital status (dead or alive; date of death when applicable) at the end of the study from publicly available sources, in accordance with local regulations. Knowledge of the vital status at the end of the study for all subjects is crucial for the integrity of the study.

See Table 1 for data to be collected at the time of study discontinuation and follow-up and for any further evaluations that need to be completed. All study treatment and treatment diaries should be returned by the subject.

Study procedures and their timing are summarised in Table 1.

The investigator will ensure that data are recorded in the eCRFs. The Web Based Data Capture (WBDC) system will be used for data collection and query handling.

The investigator ensures the accuracy, completeness, legibility, and timeliness of the data recorded and of the provision of answers to data queries according to the Clinical Study Agreement. The investigator will sign the completed eCRFs. A copy of the completed eCRFs will be archived at the study site.

Immediate safety concerns should be discussed with the sponsor immediately upon occurrence or awareness to determine if the subject should continue or discontinue study treatment.

Adherence to the study design requirements, including those specified in Table 1, is essential and required for the conduct of the study.

All screening evaluations must be completed and reviewed to confirm that potential subjects meet all of the eligibility criteria. The investigator will maintain a screening log to record details of all screened subjects and to confirm eligibility or record the reasons for screening failure, as applicable.

Procedures conducted as part of the subject's routine clinical management (e.g. blood count) and obtained before signing of the ICF may be utilised for screening or baseline purposes provided the procedures met the protocol-specified criteria and were performed within the time frame defined in Table 1.

Repeated or unscheduled samples may be taken for safety reasons or due to technical issues with the samples.

8.1 Efficacy assessments

Planned time points for all efficacy assessments are provided in Table 1.

8.1.1 Tumour response

In 2013, consensus recommendations for the imaging of PN were issued by an international working group (REiNS) who recommended MRI volumetric tumour assessment as preferable to all other MRI analysis techniques. MRI with volumetric analysis is recommended to sensitively and reproducibly evaluate changes in tumour size in clinical studies. Volumetric analysis requires adherence to specific imaging recommendations and a 20% volume change was chosen to indicate a decrease or increase in tumour size.

CONFIDENTIAL AND PROPRIETARY 60 of 183

Images, including unscheduled visit scans, will be collected on an ongoing basis and sent to an AstraZeneca-appointed imaging Contract Research Organization (CRO) for QC, storage, and for Independent Central Review (ICR). The details about target lesion location and non-target lesion location (if relevant) will also be collected to insure the independent reviewer also follow the most clinically relevant PN. Digital copies of all original scans should be stored at the Investigator site as source documents. Electronic image transfer from the sites to the CRO is strongly encouraged. An independent central review of images will be performed at the discretion of AstraZeneca. Results of these independent reviews will not be communicated to Investigators, and results of Investigator tumor assessments will not be shared with the central reviewers. The management of patients will be based upon the results of the tumor assessments conducted by the Investigator.

Extent of PN in patients with NF1 can be very substantial, and may not allow for all lesions to be followed using 3D-MRI. Prior to starting treatment on this study, the investigator must select the target PN. The target PN defined as the most clinically relevant PN that is also measurable and either typical or nodular (ie not a solitary nodular lesion). If there is a second PN that is also considered clinically relevant, the investigator may select this as a non-target lesion; only one non-target lesion can be selected. Non-target lesions must also be-measurable and either typical or nodular. Both the investigator and AstraZeneca-appointed imaging Contract Research Organization (CRO) will measure the-target PN and non-target PN (if applicable).

A site imaging specialist will be appointed and trained on performing the assessments for the study.

Screening imaging evaluation:

- Identify and select the inoperable target PN (plus a maximum of 1 additional nontarget PN) for 3D MRI evaluation. Should there be more than 2 inoperable PNs that meet the criteria for selection, the 2 most clinically relevant PNs will be followed by 3D MRI analysis.
- Perform MRI sequences on the selected index lesions as outlined in the MRI acquisition protocols.

On study imaging evaluation:

Unless clinically indicated otherwise, and as defined in Table 1, 3D volumetric MRI of the target and nontarget PNs should be performed at every 4 cycles (16 ± 1 weeks) relative to the date of first dose for the first 2 years (24 cycles). From the end of Cycle 24, tumour assessments will be performed every 6 cycles (24 ± 1 weeks), as long as the subject remains on study treatment or until disease progression. Subjects who discontinue study treatment due to reasons other than disease progression will continue to undergo tumour assessments for

approximately 1 year, if clinically applicable, and the assessment schedule should continue per the regular tumour assessment interval.

- Complete response (CR): disappearance of the target lesion.
- PR: decrease in the volume of the target PN by 20% or more compared to baseline. The PR is considered unconfirmed at the first detection and confirmed when observed again at a consecutive scan within 3 to 6 months.
- Stable disease: insufficient volume change to qualify for either PR or PD.
- PD: increase in the volume of the target PN by 20% or more compared to baseline or the time of best response after documenting a PR. The appearance of new PN (with the exception of new discrete subcutaneous neurofibromas as noted below) or unequivocal progression of an existing nontarget PN is also considered PD. In this study unequivocal progression is defined as an increase in the volume of the non-target PN by 20% or more compared to baseline.

The clinical appearance of new discrete subcutaneous neurofibromas does not qualify for disease progression. Worsening of existing symptoms or the appearance of new symptoms that persist for more than 7 days and that are felt to be definitely related to the PN should be evaluated by repeating the MRI. Subjects should not be classified as having PD solely on the basis of new or increased symptoms

Some subjects may have incomplete MRI scans during the follow-up visits and this has the potential to lead to partial volume measurements, which may not be consistent with the baseline measurements. As such, further information on how to approach these partial volumes will be provided in the site imaging analysis guideline.

Subjects who have completed any protocol-derived therapy (as little as 1 dose) will be considered evaluable for response.

Subjects who discontinue study treatment due to reasons other than disease progression will continue tumour assessments for approximately 1 year, if clinically applicable.

8.1.2 Disfigurement

Consenting subjects will have photographic documentation of visible PNs according to Table 1. Photography should be performed at screening and then at the end of Cycles 8, 16 and 24 as long as the subject remains on treatment. All photographs at each time point should be taken from the same distance, if possible using similar lighting and camera settings. Baseline photographs should be present at the time of follow-up photography to allow for the best possible comparison.

CONFIDENTIAL AND PROPRIETARY 62 of 183

Detailed recommendations for photography techniques are provided in the photography manual.

8.1.3 Clinical outcome assessments (COAs)

COAs, an umbrella term referring to all outcomes and symptoms, can be reported directly by the subject (patient-reported outcomes), by a clinician (clinician-reported outcomes) or by an observer (observer-reported outcomes). In the current study, both patient-reported outcomes and observer-reported outcomes will be used. COA will be measured in accordance with Table 1. Copies of each of the assessments used are included in Appendix I.

Baseline clinical outcome assessments should be performed prior to and as close to the first dose of selumetinib as possible (PGIC should not have any baseline assessments). Post-baseline assessments should be performed at the end of each cycle up to the end of Cycle 4, every 2 cycles up to the end of Cycle 12, every 4 cycles up to the end of Cycle 24, and every 6 cycles thereafter, as long as the subject remains on study treatment. Clinical outcome assessments will be performed electronically using on-site tablets.

Clinical outcome evaluation questionnaire	Respondent	Relevant PN morbidity at enrolment	Age
FLACC	Parent/guardian-reported	All PN	3 years
Faces pain scale	Self-reported	All PN	4 to 17 years
NRS-11	Self-reported	All PN	Adults
PII	Self-reported Parent/guardian-reported	All PN	8 to 17 years Adults 5 to 17 years
Pain medication survey	Self-reported on paper in the adult cohort and Parent/guardian-reported on paper in the paediatric cohort	All PN	All subjects
PedsQL	Self-reported Parent/guardian-reported	All PN	5 to 7 years 8 to 12 years 13 to 17 years 3 to 4 years 5 to 7 years 8 to 12 years 13 to 17 years
EORTC QLQ-C30	QLQ-C30 Self-reported		Adults

Table 8Overview of eligible subjects completing clinical outcome
assessment questionnaires, by age of patient and respondent

CONFIDENTIAL AND PROPRIETARY

Clinical outcome evaluation questionnaire	Respondent	Relevant PN morbidity at enrolment	Age
PlexiQoL	Self-reported	All PN	Adults
PROMIS (mobility)	Self-reported Parent/guardian-reported	All PN	8 to 17 years 5 to 17 years
PROMIS (upper extremity function)	Self-reported Parent/guardian-reported	All PN	8 to 17 years 5 to 17 years
PROMIS (Physical Function – Short Form 8c 7-day)	Self-reported	All PN	Adults
PGIS	Self-reported Parent/guardian-reported	All PN	8 to 17 years Adults Up to 17 years
PGIC	Self-reported Parent/guardian-reported	All PN	8 to 17 years Adults Up to 17 years

Table 8Overview of eligible subjects completing clinical outcome
assessment questionnaires, by age of patient and respondent

EORTC QLQ-C30=European Organisation for Research and Treatment of Cancer Quality of Life Questionnaire Core 30; FLACC=Face, Legs, Activity, Cry, Consolability; NRS=Numeric Rating Scale; PedsQL=Paediatric Quality of Life Inventory; PGIC=patient's global impression of change; PGIS=patient's global impression of severity; PII=Pain Interference Index; PlexiQoL=plexiform neurofibromas quality of life scale; PN=plexiform neurofibroma; PROMIS=Patient-Reported Outcomes Measurement Information System.

8.1.3.1 Pain

The effect of selumetinib on pain will be evaluated using the FLACC scale (children aged 3 years), Faces pain scale - revised (children aged 4 to 17 years), NRS-11 (adult cohort only), PII (adult cohort; self- and parent-reported in the paediatric cohort) and pain medication survey (all subjects).

8.1.3.1.1 FLACC pain scale (3 years)

The FLACC scale is an observer-reported measurement used to assess pain in children aged from 2 months to 7 years, or for individuals that are unable to communicate their pain. In this study, parents will receive a short training on how to do the assessments of pain for their child. The scale is scored from 0 to 10, with 0 representing no pain. The scale has 5 criteria (face, legs, activity, cry, and consolability), which each are assigned a score of 0 to 2 (Merkel et al 1997). In this study, the FLACC scale will be used to assess pain in children 3 years of age.

8.1.3.1.2 Faces pain scale - revised (4 to 17 years)

The Faces pain scale - revised is a self-reported measure of pain intensity developed for children. Facial images depicting no pain (score of 0) to very much pain (score of 10) are

CONFIDENTIAL AND PROPRIETARY 64 of 183

presented to the child, who will then pick the face that matches their own discomfort over the past week, giving a score. The scale shows a close linear relationship with visual analog pain scales across the age range of 4 to 16 years. It is easy to administer and requires no equipment except for the photocopied faces (Hicks et al 2001). In this study, the Faces pain scale will be used to assess pain in children aged from 4 to 17 years of age. If subjects have difficulties reading, it is permissible for site staff to read the instructions to the subject and point to the faces as they read the instructions. If a subject has difficulties remembering the worst pain they had the past week, instructions should be given to assess the worst pain they had today.

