	 PFS is defined as the time from the date of first dose until progression per REiNS criteria, as assessed by the investigator and independent central review, or death due to any cause. TTP is defined as the time from the date of first dose until progression per REiNS criteria, as assessed by the investigator and independent central review. TTR is defined as the time from the date of first dose until the date of first documented response (which is subsequently confirmed), as determined by the investigator and independent central review. 	
To evaluate the effect of selumetinib on pain in Chinese paediatric and adult subjects with NF1 and inoperable PN	 FLACC scale (3 years of age). Faces pain scale - revised (4 to 17 years of age). NRS-11 (adult cohort). PII (adult cohort; self- and parent-reported in the paediatric cohort). Pain Medication Survey (self-reported in the adult cohort; parent-reported in the paediatric cohort). 	
To determine the effect of selumetinib on HRQoL	 PedsQL (paediatric cohort; self- and parent-reported). EORTC QLQ-C30 and PlexiQoL (adult cohort). 	
To determine the effect of selumetinib on physical functioning	 PROMIS (upper extremity; self- and parent-reported in the paediatric cohort). PROMIS (mobility; self- and parent-reported in the paediatric cohort). PROMIS Physical Function - Short Form 8c 7-day (adult cohort). 	
Exploratory objectives:	Endpoints:	
To evaluate PGIS of symptoms	• PGIS (adult cohort; self- and parent-reported in the paediatric cohort).	

Table 2Study objectives

Table 2Study objectives

To evaluate PGIC in symptoms	•	PGIC (adult cohort; self- and parent-reported in the paediatric cohort).		
To determine the effect of selumetinib on disfigurement	•	Photographic evaluation.		
Safety objective: contained within the primary objectives.				

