8.1.3.6 Administration of COAs

Baseline eCOAs should be completed at the site on Cycle 1 Day 1 before dosing using an eCOA site tablet. Thereafter, subjects should complete the eCOAs at the site at scheduled visits. A web-based system will be used if the device is not available.

All assessments should be completed according to the following parameters:

- Without assistance from site staff or anyone else and according to the study SoA. However, if the subject has difficulties reading, the site staff can read the instructions to the subject.
- Before any other study procedures are conducted at a given visit
- Before being seen by a study nurse or physician

Each study center must allocate the responsibility for the administration of the COAs to a specific individual (e.g., a research nurse or study coordinator) and, if possible, assign a backup person to cover if that individual is absent.

The investigator will arrange for relevant training in the set-up of the site tablet and train subjects in how to respond to the eCOAs. The significance and relevance of the COA data should be explained carefully to subjects so that they are motivated to respond.

The following guidelines should be followed:

- The following order for completion should be ensured (and the eCOA tablet should be programmed accordingly):
 - Pediatric cohort: FLACC or Faces Pain Scale (depending on age), PII, PROMIS Mobility, PROMIS Upper Extremity, PedsQL, PGIS, PGIC
 - Adult cohort: NRS-11, PII, PROMIS Physical Function, EORTC-QLQ-C30, PlexiQoL, PGIS, PGIC
- eCOA completion must be done by the subject in private and site staff should ensure that subjects have a quiet place to complete the assessments.
- Throughout the study, subjects will continue filling in the same age-specific versions of the instruments as they completed at baseline.
- In the adult cohort, responsible physician will select the target tumor for which subjects will assess the pain intensity. The target tumor will be selected from a prespecified list of body locations on the eCOA tablet before subjects start doing the assessments.

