9.4.4.1.2 Faces pain scale – revised (4 to 17 years)

The Faces pain scale will be assessed as scheduled in Table 1. Change from baseline will be derived for each visit.

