9.5.4.1.2 Faces pain scale - revised (4 to 17 years)

Descriptive statistics for the Faces pain scale and change from baseline will be provided for each visit. A line graph with mean values/mean change from baseline values and corresponding 95% CI will be presented. Other analyses may be performed as appropriate. Further details will be provided in the SAP.

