Appendix I Clinical outcome assessments

These PRO questionnaires are for information purposes and representation only and serve as an example of the questionnaire to be used in the study.

FLACC scale

Categories	Score 0	Score 1	Score 2		
Face	No particular expression or smile	Occasional grimace or frown, withdrawn, disinterested	Frequent to constant frown, clenched jaw, quivering chin		
Legs	Normal position or relaxed	Uneasy, restless, tense	Kicking, or legs drawn up		
Activity	Lying quietly, normal position, moves easily	Squirming, shifting back and forth, tense	Arched, rigid, or jerking		
Cry	No cry (awake or asleep)	Moans or whimpers, occasional complaint	Crying steadily, screams or sobs, frequent complaints		
Consolability	Content, relaxed	Reassured by occasional touching, hugging, or being talked to, distractable	Difficult to console or comfort		

FLACC Pain Assessment Tool

Pediatric Nursing 23(3), 293-297. © 2002, The Regents of the University of Michigan. All Rights Reserved.

E-code:

Assessment Date: _____ Enter FLACC Total Score:____

Assessment Time:

Initials of person administering the assessment:

Faces Pain Scale - Revised

Instructions

These faces show how much something can hurt. The face to the left shows no pain. The faces show more and more pain up to the right face - it shows very much pain. Please choose the face that shows the worst pain you had during the past week.

Source: Adapted from Hicks et al 2001.

Adult Pain Questionnaire

(Self-report form for adults)

Numeric Rating Scale - Pain Intensity

Below are some questions about how much you hurt. The first two questions are about how much your plexiform neurofibroma tumor or tumors hurt and the last question is about how much you hurt from all kinds of pain.

Below are lines with numbers from 0 to 10 where 0 means no pain and 10 means the worst pain you can imagine.

1. The doctor has picked the plexiform neurofibroma tumor in your body to measure for this study. We call this the "target tumor." We will ask you to tell us about that same tumor pain at each study visit.

Target tumor: _____

Please circle the one number that best describes the pain from your target tumor at its worst during the past 7 days.

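### The Faces pain scale permits a change of recall window from past week to today without recording it or matching it to baseline, so change scores may mix two different quantities

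*Protocol*

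**What the plan says.** Protocol Section 8.1.3.1.2 describes a self-reported 0-10 scale in which the child is shown faces, "who will then pick the face that matches their own discomfort over the past week, giving a score". The form reproduced in Appendix I has the same window and specifies the worst pain: "Please choose the face that shows the worst pain you had during the past week".

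Section 8.1.3.1.2 then adds a conditional fallback. Its trigger is "If a subject has difficulties remembering the worst pain they had the past week", and its instruction is "instructions should be given to assess the worst pain they had today". No criterion for the difficulty is given.

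Section 8.1.3.6 has one rule on consistency over time: "Throughout the study, subjects will continue filling in the same age-specific versions of the instruments as they completed at baseline". It fixes the age version of the instrument and does not mention the recall window.

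For the analysis, Section 9.4.4.1.2 says "The Faces pain scale will be assessed as scheduled in Table 1. Change from baseline will be derived for each visit", and Section 9.5.4.1.2 says "Descriptive statistics for the Faces pain scale and change from baseline will be provided for each visit", with line graphs of means or mean changes and 95% confidence intervals. Neither refers to the window. Section 3 (Table 2) lists "Faces pain scale - revised (4 to 17 years of age" among the endpoints for the secondary pain objective.

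**The concern.** The worst pain of a week and the worst pain of today are different quantities. The first is a maximum over seven days, the second a maximum over one. It may be less than one, because Section 8.1.3.6 has these assessments completed before any other procedure at the visit. A change score that subtracts one from the other contains the difference between the two definitions as well as any change in pain.

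The fallback is worded for the assessment at hand and is not tied to what was done at baseline, so a child may use one window at baseline and the other later. The study has no control arm in which the same artefact could occur and cancel. If the window is not captured when the score is taken, no later analysis rule can identify the affected pairs.

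At stake is the reading of mean change on the only self-reported pain-intensity scale that the secondary pain objective offers for ages 4 to 17. For comparison, the adult NRS-11 (Section 8.1.3.1.3) uses a 7-day window with no such fallback.

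**Working it through.** **No figure to reproduce.** Section 9.1 plans no hypothesis test, and the protocol gives no expected pain level, variability or effect size for this scale. Direction can be settled by logic; size can only be illustrated.

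**Direction.** Let D1, ..., D7 be a child's worst pain on each of seven days, with D7 today. Then D7 ≤ max(D1, ..., D7), with equality only if no earlier day was worse. If the pain process is the same at baseline and follow-up, the expected change is:

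- week at baseline, today later: E[D7] − E[max] ≤ 0, an apparent improvement;
- today at baseline, week later: the same size with a positive sign, an apparent worsening;
- same window at both visits: 0.

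**Size for one switching child (illustrative).** All inputs here are assumptions: normal daily worst pain with mean 2 or 4, daily SD 1 to 3, equal correlation ρ between any two days, and scores rounded to 0, 2, 4, 6, 8 or 10. Before rounding and truncation at 0 and 10, the gap is

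E[max] − E[D7] = 1.352 × SD × √(1 − ρ),

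where 1.352 is the expected maximum of seven independent standard normal values. A simulation of 200,000 children per scenario adds the rounding and truncation:

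| Daily SD | ρ | Formula | Simulated, mean 4 | Simulated, mean 2 |
|---|---|---|---|---|
| 1 | 0.9 | 1.352 × 1 × 0.316 = 0.43 | 0.42 | 0.42 |
| 2 | 0.9 | 1.352 × 2 × 0.316 = 0.86 | 0.84 | 0.75 |
| 2 | 0.5 | 1.352 × 2 × 0.707 = 1.91 | 1.89 | 1.77 |
| 2 | 0.3 | 1.352 × 2 × 0.837 = 2.26 | 2.25 | 2.12 |
| 3 | 0.3 | 1.352 × 3 × 0.837 = 3.39 | 3.17 | 2.94 |
| 1 to 3 | 1.0 | 0 | 0 | 0 |

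The range is about 0.4 to 3 points, or zero when pain is the same every day. A child who scores 0 on every day also shifts by 0 whichever window is used.

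**Size for the cohort mean (illustrative).** Section 9.2 plans about 16 paediatric subjects; any 3-year-olds use FLACC, so the Faces denominator may be smaller. If k of 16 switch in the same direction, the mean moves by k/16 times the individual shift. For k = 4 this runs from 0.42 × 4/16 = 0.1 to 3.17 × 4/16 = 0.8 points. Switches in opposite directions offset each other in the mean but still add spread. The documents give no basis for any value of k.

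**The case against.** The strongest reply is that the clause is a narrow and sensible accommodation. It applies only when a child has difficulty remembering, and is not a free choice at each visit. If the difficulty reflects age or cognition, the same child will probably use the same window throughout, and no artefact arises. This stands: the point concerns only children whose window changes, and their number is unknown.

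A reader might infer that the clause tilts the results in the drug's favour. The documents do not support that. They give no reason to expect week-to-today switches to be more common than the reverse. Recall may improve as a child grows older over 24 cycles, and that would produce apparent worsening.

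The sizes are also open to challenge. Inclusion criterion 5 (Section 5.1) does not require pain, so some children may sit at or near zero, where the shift vanishes. The model further assumes that a child using the weekly window reports the true weekly maximum, and the children nearest to the fallback are the least likely to do so. The figures are therefore illustrations, not estimates.

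Finally, Section 9.5.4.1.2 leaves further detail to the SAP, which is not at hand, and it may well say which pairs enter the change score. That is fair for the derivation rule. It does not answer the collection instruction, which stands in the protocol and does not ask for the window to be noted.

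**Conclusion.** The concern holds as one of measurement consistency. Following Section 8.1.3.1.2 as written can put two non-comparable quantities into one change score, and nothing in the protocol lets the analyst recognise when this has happened. The sign for a given switch follows from logic alone. The net direction across the cohort is unknown, and the size (about 0.4 to 3 points for a switching child, zero for one with absent or constant pain) depends on assumed daily SDs of 1 to 3 and day-to-day correlations of 0.3 to 0.9.

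The reach is limited. A reader might take this for the main pain endpoint of the paediatric cohort, but Section 3 lists the Faces scale as one of several secondary pain measures and ranks none first. The Pain Interference Index also covers pain in children, on a 7-day window, though it measures interference and not intensity. The exploratory PGIS asks about pain severity today. The Faces analysis is descriptive, and the primary safety and pharmacokinetic objectives are unaffected. The point is still worth acting on, because the correction is cheap and the comparison with baseline is uncontrolled.

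**What to change.** In Section 8.1.3.1.2, require the recall window used to be recorded at every Faces assessment, and ask that later visits use the child's baseline window where possible. Keep the fallback for a child who cannot recall the week at a later visit, and flag that score. Locking the window strictly at baseline would leave such a child with no usable answer.

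In Section 9.5.4.1.2 (or the SAP, if it holds the derivation rules), base the main summary of change from baseline on pairs with matching windows. List the mixed-window pairs and include them in a sensitivity summary.

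The cost is a short addition to the protocol, one tick-box on the tablet and one derivation rule. The downside is that a few change scores leave the main summary, mostly from children with poor recall. In a cohort of about 16 that loss is selective, which is why the sensitivity summary should sit beside it.
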